Currently, patients being treated in rehabilitation settings after acute stroke who experience difficulties in achieving sufficient or restful sleep are treated with environmental adaptations (such as minimizing nighttime interruptions in room) and frequently, with pharmacological agents. One commonly used agent, trazodone, is a hypnotic antidepressant with sedative qualities. Trazodone is frequently used because it is viewed as being effective and relatively safe; however, this class of medications is known to alter sleep architecture resulting in more time in light sleep and reduced amounts in deep restorative sleep. Additionally, trazodone has well documented carryover effects that are detrimental to stroke recovery. These carryover effects include deficits in short-term memory, verbal learning, equilibrium, and arm muscle endurance³. Most importantly, trazodone has been shown to significantly interfere with sleep-dependent consolidation of cortical plasticity³. These effects are in stark contrast to the goals of rehabilitation patient who requires neuronal plasticity for his or her recovery.

Conversely, cranial electrical stimulation (CES) is a safe method tested in a number of pilot studies to promote deep, restorative sleep that is seldom used. There are many potential advantages to using CES in place of medications, including safety. CES has few notable side effects and has none of the drug-drug interactions that are commonplace in pharmaceuticals. CES is FDA approved to treat insomnia, depression, anxiety and pain. Additionally, CES has been shown to increase learning, consolidation of memory, creativity and mood. Patients who use CES report feeling calm, focused, and relaxed. Side effects of CES are extremely rare and the known risks of CES are minimal and mild in nature⁴. Skin irritation may occur at the site of sponge electrode placement when sponges deteriorate or if the sponges are not thoroughly wet before use. The device manufacturer also cites a mild headache or dizziness that may occur during use and ceases when the device is turned off. Such reactions are very rare.

STU072016-005, [name], FormA-ResearchProtocol, Mod_8, 10-30-18

Version <2>

Page 1 of 9

Despite the potential benefits of CES over medications such as trazodone, this technology is seldom used. One reason for this is the paucity of rigorous research proving its benefit. There have been many studies since the technology was first introduced in the 1950's, but there are very few modern well-controlled and powered studies with conclusive evidence for or against CES as a treatment for sleep. Nearly all studies examined cite deficits in power or adequate blinding. Furthermore, there are no studies using CES as a treatment for insomnia in stroke patients. The purpose of this study is to determine if CES is a reasonable first line alternative to the current standard of care (SOC) which relies on the use of trazodone for patients with subacute stroke. This objective will be answered by addressing the following:

- Specific Aim 1: To determine if stroke patients with insomnia who receive CES treatment sleep more hours than stroke patients treated with sham CES.
Hypothesis: Stroke patients with insomnia who are treated with CES will accumulate more sleeping hours than patients who are treated with sham CES.
- Specific Aim 2: To determine if stroke patients with insomnia who receive CES treatment have better sleep efficiency than stroke patients treated with sham CES.
Hypothesis: Stroke patients with insomnia who are treated with CES will demonstrate significantly better sleep efficiency than stroke patients treated with shame CES.

Our study will take place at Zale Lipshy Hospital and Parkland Hospital in Dallas, TX. The study will enroll 85 stroke patients who score 7 or higher on the Insomnia Severity Scale. Patients will be randomized to a control group or CES treatment group. Patients will receive CES or sham CES for 7 days after a 24-hour washout period. Objective and subjective sleep assessments will be conducted daily during the 7-day study period. Endpoints will be total time spent sleeping, sleep efficiency and daytime drowsiness.

The known risks of CES are minimal and mild in nature. They include potential for headache, irritation at the site of electrode placement and dizziness. These adverse reactions are rare and in most cases there are no immediate or delayed side effects.

Compared to the known adverse reactions of the current standard of care, trazodone, the known adverse events of CES are considerable less severe. Known adverse reactions of trazodone include black box warnings for risk of suicidal thinking and behavior in patients less than 24 years of age. In addition, trazodone has a long list of potential adverse events, most involving anticholinergic effects (sedation, dry mouth, blurred vision) and must be used with caution with platelet inhibitors, MAO inhibitors, and other drugs causing prolonged QT intervals.

2. Background

Cranial Electrical Stimulation (CES) is safe and potentially effective way to promote restorative sleep without the carryover effects of pharmaceuticals. CES introduces miniscule electric currents, often no more than 1-2 mA to the head of individuals suffering from depression, anxiety and insomnia^{5, 6}. While the exact mechanism is unknown, it is generally accepted that CES acts through direct action on the brain at the limbic system, thalamus, hypothalamus, and reticular activating system⁷. In these areas, the penetrating micro-currents stimulate the release of neurotransmitters such as serotonin, beta-endorphin, and GABA (FW manual). The overall effect of this is increased alpha brain wave activity and decreased delta wave activity which translates to feelings of serenity, relaxation and reduced agitation⁷. In addition to insomnia, CES is FDA approved to treat anxiety and depression, much like trazodone which is the most commonly used hypnotic at this time.

Trazodone is widely used, but its mechanism of action is not fully understood either. What is known is that it exerts its antidepressant effect as a serotonin (5-HT₂) antagonist and reuptake inhibitor⁸.

Serotonin is an important chemical neurotransmitter which has functions in both the central nervous system and the peripheral nervous system. Alterations in levels of serotonin by trazodone therefore cause widespread effects as detailed previously.

Low intensity current has the potential to modulate the release of neurotransmitters but since the reuptake mechanisms are not affected there is little risk in overstimulation. The CES device we will be using is an alternating current (AC) stimulator. This means that each electrode rapidly switches between being the cathode and the anode. The electronic waveform generated from the device is a 15,000Hz square wave carrier which is rectified, varying from zero to a maximum of 4 milliamperes. This device is a bipolar version of a TENS device, where there is a brief burst (50 milliseconds) of positive energy [above the zero axis], followed by a 16.7 millisecond "OFF" time, followed by a 50 millisecond burst of negative energy [below the zero axis], followed by a 16.7 millisecond "OFF" time. In this manner consecutive positive burst and off time is followed by an equal and opposite negative burst and off time, thereby generating alternating current⁴.

The output amplitude is 0-4 milliamperes at a cycling rate of 15/500/15,000 Hz with a pulse width of 33 microseconds. The maximum charge per pulse is 0.13 microcoulombs. The output voltage is variable from zero to 40 volts and then the voltage limited, first positive and then negative. This allows for load impedances of up to 10,000 ohms to be able to have a constant current of up to 4 milliamperes⁴.

It is well described how depolarizations of neuronal membranes lead to release of chemical neurotransmitters; therefore, one could potentially modulate the cerebral chemical environment by electrical intervention. Research from the University of Texas at Austin indicated that indeed external electrical stimulation can readily alter the deep brain electrical environment. In their 1996 publication, Ferdjallah et al reported that 1 mA of current from CES reaches the thalamic area at a radius of 13.30 mm and may facilitate the release of neurotransmitters⁹.

The structures that CES is believed to affect are centrally located in the brain and are known to be involved in regulation of emotions. These subcortical brain structures are the reticular activating system, thalamus, and hypothalamus, and the limbic system. As the low intensity external charge supplied by CES reaches these deep brain structures there is a measurable physiologic result. Researchers from the University of North Texas used electroencephalogram (EEG) to show that CES is able to increase alpha brain waves (8–12 Hz) and decrease delta (0–3.5 Hz) and beta (12.5–30 Hz) brain waves. Increased alpha correlates with improved relaxation and increased mental alertness or clarity. Decreased delta waves indicate a reduction in fatigue. Beta-wave reductions between 20 and 30 Hz correlate with decreases in anxiety, ruminative thoughts, and obsessive/compulsive-like behaviors¹⁰.

While CES has been shown to be clinically effective in multiple studies, there are equal numbers of studies showing no effect or an indeterminate effect¹¹. In nearly all these studies the researchers call for further study with higher patient numbers and rigorous blinding. This study will be an extension of previous work showing potential efficacy in sleep, while introducing a new population in subacute stroke patients. We anticipate our findings will benefit future patients by providing an alternative to hypnotics which may have negative effects that are detrimental to the recovery of the stroke patient.

3. Concise Summary of Project

This will be a double blinded randomized clinical trial carried out at Zale-Lipshy and Parkland Hospital Inpatient Rehabilitation Facilities. Acute stroke patients with insomnia, identified by the Insomnia Severity Index (ISI), and who choose to participate in this study will be randomized to CES or sham CES. Patients who do not feel they are getting adequate sleep but want to continue in the study will be given the option to receive the standard of care medication as a rescue starting on the 3rd night.

Patients will receive treatment with a Fisher-Wallace CES device or Sham CES. Treatment with CES will be for 20 minutes once a day, and the treatment period will be for 7 days. Patients will be allowed to increase the intensity of the device from the suggested starting point of level 2 if they feel no improvement in sleep on night 1. Groups will be monitored with a wrist worn actigraph that records the patient's activity for the duration of the period of study and provides data on sleep latency, time spent asleep, and sleep efficiency. The outcome measures will be total minutes/hours of sleep, sleep efficiency and subjective reports of drowsiness using the Karolinska Sleepiness Scale. Actigraphic data will be collected 24 hours a day for 7 days. The total length of study will be 4-12 months with a target N of 100 consented individuals and 85 participants. Patients will be allowed to exit the study at any time on their own choosing. To minimize loss of subjects, patients will have the option to choose SOC rescue starting on the third night. Patients who choose the SOC rescue will continue to be monitored with an actigraph for data collection purposes.

The investigator should discontinue study participation for a given subject or withdraw the subject from study if he/she believes that continuation would be detrimental to the subject's well-being. A subject can decide to withdraw from the study at any time and for any reason.

4. Study procedures

This randomized controlled trial is designed to meet two study objectives related to quality of sleep and daytime drowsiness.

Demographic data will be collected from the hospital record and will include age, gender, type of stroke, self-reported history of insomnia or other sleep disorder, prior use of sleep medications, in-hospital use of sleep medications, co-morbid medical conditions.

[figure not shown]
Patients admitted to inpatient rehabilitation (IPR) who consent to the study will undergo an overnight washout period before initiation of CES or sham treatment. This allows for any sleep medication they might have received while in acute care to be metabolized and leave their system. On their admission day, day 0 (d0) patients will be asked if they want to participate in our study. If they choose to participate and meet medical inclusion criteria, they will be tested with ISI. Patients who meet the full criteria will not receive sleep medication or CES on their first night.

The study will begin on day 1 (d1) with the patient receiving 20 minutes of CES/sCES in the morning. This time will be distraction free without the entrance of laboratory technicians, nurses, housekeeping or other staff members. When this period is complete, they will participate in usual care. At midday they will be asked to complete the Karolinska Sleepiness Scale (KSS). The patient will wear the actigraph throughout the study. This procedure will be repeated for 7 treatment days. All procedures will be carried out by research team members or a trained nurse.

The intensity of the CES will begin on setting 2, standard setting recommended by the device manufacturer, and the patient will have the option to increase the intensity to setting 3 on the second treatment day if they feel they did not receive any benefit from the device.

If the patient does not feel they are getting adequate sleep the patient may choose to opt out of CES/sCES treatment and receive the standard of care medication for the remainder of the study. Patients who choose the SOC rescue will continue to be monitored with the actigraph. A patient may choose to leave the study at any time.

We will collect information on side effects for the CES treatment during the 7 days of the study.

Methods of assigning patients to treatment groups and blinding

Patients will be randomized to the active or sham treatment group using an online randomizer, Research randomizer (www.randomizer.org). A list of random numbers will be generated prior to the study. Patients will be assigned a random number in the order that the generator produces. All even patients will be assigned to the control group; odd numbered patients will be assigned to the treatment group.

Procedural responsibilities and oversight

Nursing staff at UTSW will be educated how to administer the CES and asked to help distribute and collect the Karolinska Sleepiness Scale questionnaire. Photos of proper placement and instructions will be posted in subjects' rooms for reference. Researchers affiliated with this project will apply and remove the actigraph watches and be responsible for data acquisition, cleaning and charging of the devices. Researchers affiliated with the study will be responsible for ensuring CES is delivered to the appropriate patients on the days required per protocol. Research personnel will be responsible for all study-related activities at Parkland.

5. Inclusion criteria

To be eligible for inclusion in this study, subjects must fulfill all of the following criteria at screening.

1. Written informed consent must be obtained.
2. Patients must be admitted to inpatient rehab.
3. Patients must have a documented acute stroke (ischemic, hemorrhagic or embolic).
4. Patients must have at least one fully functional arm which can be used to record actigraph data via a wrist worn actigraph device.
5. Subjects must Score a 7 or higher on the ISI.
6. Patients must be able to communicate consent and/or desire to discontinue the study.

6. Exclusion criteria

Subjects fulfilling any of the following criteria at screening will not be eligible for inclusion in this study.

1. Demand or sensing type cardiac pacemaker.
2. Known uncontrolled seizure disorder.
3. Current history of vertigo.
4. Need for continuous O2.

5. Inability to communicate or provide consent.
6. Restricted use or absence of both arms.

7. Sources of research material

All data will be collected prospectively through a wrist-worn actigraph and a sleep questionnaire. This data will be used specifically for research purposes. Demographic data will be collected from the hospital chart.

8. Recruitment methods and consenting process:

We will use verbal recruitment process for the study. The attending and resident physicians will be educated about the study and asked to identify patients who may be appropriate. A member of the research team will explain the risks, benefits and rationale for the study to patients who meet inclusion criteria. Patients will be enrolled when they arrive on the rehabilitation floor if they choose to participate. Consent will be attained via a written document in the subject's primary language (English or Spanish).

The research team will protect subjects' privacy by conducting all study related verbal interactions with the subject in a closed room, such as the patient's room. For confidentiality, each subject screened will be assigned a unique identification number (ID#). Subjects will only be identified by the unique ID # in the data. No demographic data or personal information will be used to identify subjects. This unique ID# will be linked to subject name and will be kept in a locked file cabinet, accessible only to the research team. Only the research team will have access to the data. All data for presentations and publications will be reported as mean \pm standard error of means. Investigators will educate faculty and residents on each floor about the study to maintain privacy and compliance.

9. Potential Risks

The Fisher Wallace Cranial Electrical Stimulator is known to have the potential for very rare and mild adverse reactions. These include, skin irritation at the site of sponge electrode placement, especially if the sponges deteriorate. Per Fisher Wallace recommendations, the sponges will be replaced every two weeks to prevent contact between the skin and the metal part of the sponge receptacle. This risk will also be mitigated by ensuring the sponges are thoroughly wet before each use. In rare cases a mild headache or dizziness may occur, and should cease after stopping use of the device. Such reactions represent minimal risk.

11. Subject Safety and Data Monitoring

Study data will be accessible only to study personnel. All paper study records will be kept in a secured locked location. All electronic study data will be stored on password protected, encrypted computers; flash drives used for data storage will be encrypted. Each subject will be assigned a study number in consecutive order. The key linking the subject identifier (name and MRN) to the subject study number will be kept secure and separate from the research data. The key will be destroyed at the time that data entry and analysis is completed.

All patient information will be de-identified prior to statistical analysis. This spreadsheet will be destroyed after the data has been analyzed and PHI will not be re-used or disclosed. A link will be needed to ensure accurate collection of data on subsequent visits.

For participants who are screened and included in the study the essential documents will be filed with the individual's research file and kept for seven years.

12. Procedures to Maintain Confidentiality

The research team will protect subjects' privacy by conducting all study related verbal interactions with the subject in a closed room, such as private space in the patient's room. For confidentiality, each subject screened will be assigned a unique identification number (ID#). Subjects will only be identified by the unique ID # in the data. No demographic data or personal information will be used to identify subjects. This unique ID# will be linked to subject name and will be kept in a locked file cabinet, accessible only to the research team. Only the research team will have access to the data. All data for presentations and publications will be reported as mean \pm standard error of means.

13. Potential Benefits

There are many potential benefits to this study with both immediate and long term applications in improving sleep and minimizing the use of sedative medications during stroke recovery. Cranial Electrical Stimulation is a favorable alternative to standard of care medications like trazodone because individual participants may experience improved sleep and it is without the many side effects of these medications that increase the risk of complications. Some finding suggests that CES also increases learning, creativity and mood, and decreases anxiety, depression, and pain. It is through these mechanisms that patients will benefit immediately from this study.

In the long term, future patients may benefit from this study by potentially having an alternative first line treatment option for insomnia that does not have the negative carryover effects and plasticity reducing effects of hypnotics and sedatives. Additionally, treatment with CES offers the potential for improved functional recovery efficiency, increased patient satisfaction and increased cost effectiveness.

14. Biostatistics

Sample size was calculated based on several studies that measured the number of hours that subacute rehabilitation patients sleep in an inpatient hospital setting. Alpha levels for error probability were set at .05 for a two-tailed test with 80% power to detect a difference between means of control group compared to CES treatment group.

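### The purpose promises an answer about trazodone that a CES-versus-sham trial cannot give, and the chi-square on seven daily KSS scores should be a two-group test of a per-patient mean

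*Combined protocol and SAP*

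**What the plan says.** **Purpose.** The opening section (before Section 2, Background) gives the purpose as to "determine if CES is a reasonable first line alternative to the current standard of care (SOC) which relies on the use of trazodone" in subacute stroke. It continues: "This objective will be answered by addressing the following". Two aims follow, on hours slept and on sleep efficiency, each against sham CES.

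**Design.** Under Section 3, patients "will be randomized to CES or sham CES". The allocation paragraph in Section 4 has only a control and a treatment group, and the power statement in Section 14 is control against CES. Standard-of-care medication is an optional rescue for patients who feel they are not sleeping enough.

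**Outcomes.** Section 3 states: "The outcome measures will be total minutes/hours of sleep, sleep efficiency and subjective reports of drowsiness using the Karolinska Sleepiness Scale". It adds: "Actigraphic data will be collected 24 hours a day for 7 days". Section 4 has the KSS completed at midday on each of 7 treatment days. On the washout night before them: "Patients who meet the full criteria will not receive sleep medication or CES on their first night".

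**Analysis.** Section 14 gives a t-test for sleep time, a chi-square for the KSS, a general sentence on descriptive statistics, and an unnamed non-parametric fallback if normality fails. It does not mention sleep efficiency, although the Aim 2 hypothesis is that CES patients "will demonstrate significantly better sleep efficiency than stroke patients" on sham.

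**The concern.** Sham is a sound control for whether CES works. It cannot show how CES compares with trazodone, and the purpose says that this question will be settled. The opening section and Section 2 argue at length for CES over trazodone, so a win over sham could easily be read as a finding against the drug.

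For the KSS, a chi-square needs independent observations and ignores the order of the categories. Seven scores from one patient are not independent, and sleepiness ratings are ordered. Depending on how the scores enter, the test either overstates the evidence or loses power.

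For Aim 2, a hypothesis of significant improvement has no named test, so that analysis would be chosen after the plan was written.

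**Working it through.** **Step 1. Which comparisons are randomised.** Aim 1: CES versus sham. Aim 2: CES versus sham. Allocation: CES versus sham. Powered contrast: control versus CES. Patients randomised to standard-of-care drug: none. Rescue users select themselves, and rescue is open to both groups, so their data supply no randomised contrast. A larger sample would not change this.

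**Step 2. The plan's own figure.** The 85 participants at 80% power, two-sided .05, cannot be reproduced because no difference or SD is given. Solved backwards for 42 versus 43, the detectable difference is (1.96 + 0.842) × √(1/42 + 1/43) = 2.802 × 0.217 = 0.61 SD. This concerns CES versus sham only.

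**Step 3. The KSS under each reading.** The documents give no response categories, effect or correlation, so these are assumptions: 43 versus 42; a latent normal daily score cut into 5, 7 or 9 ordered categories; equal within-patient correlation ρ of 0.3, 0.5 or 0.7; a 0.5 SD shift on days 2-7 and none on day 1; no missing scores and no dilution by rescue. Simulated results, rounded, with ranges over category count, cut type and simulation error (three values are for ρ = 0.3 / 0.5 / 0.7):

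| KSS analysis | False positives | Power |
|---|---|---|
| Chi-square, 7 days pooled, 5-9 categories | 13-18% / 25-32% / 40-50% | not interpretable |
| Chi-square, 7 days pooled, cut in two | 18% / 25% / 32% | not interpretable |
| Chi-square, one day, 5-9 categories | no clustering inflation | 23-36% |
| Chi-square, one day, cut in two | no clustering inflation | about 44% |
| t-test, one day | no clustering inflation | about 57% |
| Chi-square, patient means split at the median | 5% | 78-81% / 65-68% / 56-57% |
| t-test, days 2-7 patient mean | about 5% | 92-94% / 81-85% / 72-75% |

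**Step 4. Hand checks.**
- *Pooled, cut in two at the median.* The correlation between binary scores is (2/π)·arcsin(ρ) = 0.194, 0.333, 0.494. The variance inflation is 1 + 6 times this: 2.16, 3.00, 3.96. The false-positive rate is P(|Z| > 1.96/√inflation) = 18%, 26%, 32%, matching the table within about a point.
- *Days 2-7 mean.* SD = √((1 + 5ρ)/6) = 0.645, 0.764, 0.866. The standardised difference 0.5/SD is 0.775, 0.655, 0.577. Power is Φ(difference/0.217 − 1.96) = 95%, 85%, 76% before any loss from categorising, slightly above the simulated figures as expected.
- *Median split of that mean.* The shares above the median are Φ(±half the standardised difference): 65% v 35%, 63% v 37%, 61% v 39%. The two-proportion normal approximation gives 80%, 66%, 55%, in line with the table.

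**Step 5. Day 1.** The first midday score follows the untreated washout night. If day 1 carries no effect, the t-test on a days 1-7 mean has 85-87%, 71-73% and 59-62% power, below the days 2-7 mean.

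**Step 6. Sleep efficiency.** The t-test sentence is limited to sleep time. The non-parametric sentence names no outcome. Only the sentence on descriptive statistics could reach efficiency, and it is not an inferential test.

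**The case against.** - **Purpose.** The aims immediately after the purpose both name sham, a reasonable alternative claims neither superiority nor non-inferiority, and no analysis against trazodone is planned. That is right, and it limits the point to the promise that the question will be answered. A reader might infer that sham is the wrong control, or that a trazodone arm or a non-inferiority design is required. The documents do not support this: sham fits both aims as written.
- **KSS reading.** Section 14 never says that days are pooled, and one chi-square on a value per patient has no clustering inflation. This stands. The 40-50% figure is the worst case of several readings, not a property of the plan.
- **Power contrast.** Setting a single-day chi-square against a multi-day t-test changes two things at once. This stands. On one day, changing the test moves power from 23-36% to about 57%; the rest comes from averaging days.
- **Rescue.** The power figures ignore it. This stands too. If, for illustration, 30% of CES patients lost the effect from day 4, the proposed test would have about 77-81%, 63% and 53% power.
- **Weight.** The KSS appears in neither Specific Aim. It is nevertheless one of three listed endpoints and has its own stated test.
- **Aim 2.** A reader might infer that Aim 2 will go untested. The text supports only that no inferential test is named.
- **Multiplicity.** A reader might infer that three endpoints inflate the trial's overall error. The plan contains no rule by which a win on any one endpoint decides the trial. Sleep time is the implied primary: it is Aim 1, the basis of the sample size, and the outcome of the only test given a threshold.

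**Conclusion.** The point holds in three limited parts.

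First, the stated purpose overreaches. The trial can show whether CES beats sham; it yields no randomised estimate relative to trazodone. This follows from the text and rests on no assumption.

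Second, the KSS chi-square is unspecified, and each of the three readings examined is inferior to a two-group test of a per-patient mean. Against the most favourable one, the median split, the gain is roughly 11 to 20 percentage points of power (for example, 92-94% against 78-81% at ρ = 0.3). Against a single-day chi-square it is larger, but partly due to averaging. Against pooling, the gain is control of the error rate. All these sizes depend on the assumed categories, shift and correlations, and rescue would lower the powers.

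Third, and lesser, Section 14 names no inferential test for sleep efficiency and does not define the per-patient summary of sleep time.

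The sham comparison of sleep time itself stands. These changes should be made, but they do not call the design into question.

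**What to change.** 1. **Opening section.** Restate the purpose as whether CES improves sleep compared with sham in stroke inpatients with insomnia. State that no conclusion relative to trazodone will be drawn, including from patients who take rescue.
2. **Section 14, KSS.** Replace the chi-square with a t-test, or the non-parametric alternative already allowed, on one pre-specified per-patient mean of the midday scores. Days 2-7 are suggested, for the reason in Step 5.
3. **Section 14, sleep outcomes.** Name sleep time as the single primary endpoint, analysed as one stated per-patient daily mean, and say whether it is night or 24-hour sleep. Apply the same two-group test to sleep efficiency as a secondary endpoint.
4. **Days after rescue.** State that all recorded days are analysed in the assigned group. The actigraph continues after rescue; say whether the KSS does too.

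**Cost.** Text edits only; sample size, visits and data collected do not change. The trial can no longer be presented as answering the trazodone question. If sleep time is not significant, efficiency is supportive only. A days 2-7 KSS mean gives up one score and any same-day effect of the first session. A 24-hour sleep measure would count daytime naps as benefit. Counting days after rescue would shrink the difference if sham patients take rescue more often.

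### The visible text schedules no actigraphy on the untreated d0 night, so sleep time and sleep efficiency have no pre-treatment value and the analysis gives up some precision

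*Combined protocol and SAP*

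**What the plan says.** **Order of events.** The opening section puts the washout before treatment: "Patients will receive CES or sham CES for 7 days after a 24-hour washout period". Section 4 has consent and the ISI on d0 and then a night without active intervention: "Patients who meet the full criteria will not receive sleep medication or CES on their first night". The next step is "The study will begin on day 1 (d1) with the patient receiving 20 minutes of CES/sCES in the morning".

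**Recording window.** Section 3: "Actigraphic data will be collected 24 hours a day for 7 days". The treatment has the same length: "the treatment period will be for 7 days". The opening section ties measurement to the same window: "Objective and subjective sleep assessments will be conducted daily during the 7-day study period". Section 4 adds: "The patient will wear the actigraph throughout the study. This procedure will be repeated for 7 treatment days". Section 3 also says that the watch "records the patient's activity for the duration of the period of study".

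**Analysis.** Section 14 compares mean sleep time between arms by a t-test, with a non-parametric alternative if normality fails. It has no baseline term, and it names no separate test for sleep efficiency.

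**Other d0 information.** The ISI (for eligibility), self-reported history of insomnia or other sleep disorder, and prior and in-hospital use of sleep medication are collected. None of these is a value of an actigraphic endpoint.

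**The concern.** Aims 1 and 2 rest on sleep time and sleep efficiency from the actigraph. A patient's own untreated sleep is a natural predictor of later sleep, and the design already contains one untreated night with the patient consented, screened and on the ward. If the watch first goes on at d1, every recorded night follows at least one CES or sham session, and that night cannot be recovered afterwards.

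At stake are the precision of the between-arm comparison, a description of how the two arms slept before treatment, and any description of change from untreated sleep. Precision matters here because the opening section itself faults earlier CES studies for inadequate power.

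**Working it through.** **1. Day count.** Washout is d0 and its night (1). Treatment is d1 to d7 (7). Total: 1 + 7 = 8 days. Actigraphy is stated as 7 days, so one day is uncovered. Section 4 starts the study on d1 and the opening section ties assessment to the 7-day study period, so the uncovered day is d0. The first session is on the morning of d1, so the first scheduled night already follows treatment. Scheduled pre-treatment nights: 0.

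**2. The plan's own figure.** Section 3 gives 85 participants. Section 14 gives two-sided alpha 0.05 and 80% power, but no difference or SD, so 85 cannot be reproduced. Working backwards with 1:1 allocation (assumed, 42.5 per arm), the standardized difference with 80% power is:
- normal approximation: (1.960 + 0.842) × sqrt(2/42.5) = 2.802 × 0.217 = 0.608
- t distribution: 0.615, used below.

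**3. Value of one baseline night.** Assume that the endpoint is the mean of seven nights (the plan does not say how nights are combined) and that any two nights on the same patient correlate by ICC. Then

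r = ICC / sqrt(ICC + (1 − ICC)/7).

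At ICC 0.1: r = 0.1 / sqrt(0.1 + 0.9/7) = 0.1 / sqrt(0.2286) = 0.1 / 0.478 = 0.209.

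Adjustment removes a fraction r² of the variance. The effective standardized difference becomes 0.615 / sqrt(1 − r²), and the sample size giving the same precision as 85 unadjusted is 85 × (1 − r²).

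| ICC (assumed) | r | Variance removed (r²) | Effective difference | Power at 85 | Equivalent N |
|---|---|---|---|---|---|
| 0.1 | 0.21 | 4.4% | 0.629 | 81.7% | 81 |
| 0.2 | 0.36 | 12.7% | 0.658 | 85.1% | 74 |
| 0.3 | 0.47 | 22.5% | 0.698 | 88.9% | 66 |
| 0.4 | 0.57 | 32.9% | 0.751 | 92.8% | 57 |

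The low end belongs in the range. The formula treats night 0 as interchangeable with later nights, but it is a first night on a new unit and may carry residual medication, while later nights may involve a higher device setting or rescue medication.

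**The case against.** **The omission is inferred.** No sentence says that the watch goes on at d1. The Section 4 figure sits just before the d0/d1 description and may show the schedule, and Section 3 speaks of recording for the whole period of study. This stands as a limit on certainty: one can say that the visible text schedules no baseline night, not that none is recorded. It does not overturn the reading, because the text starts the study on d1 and gives 7 days of recording, not 8.

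**Validity is untouched.** The aims and the t-test concern sleep under treatment, compared between randomized arms. A missing baseline does not bias that comparison. This stands in full.

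**Some pre-treatment information exists.** The ISI, insomnia history and sleep-medication use allow a partial balance check and could serve as covariates. This also stands, but they are not values of sleep time or efficiency.

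**Two stronger readings are tempting.**
- A reader might infer that the washout night will be averaged into the outcome: one untreated night in seven would shrink the effect to 6/7, and 80% power would fall to about 67% with the SD unchanged. That needs a d0 start, which Section 4 contradicts, and an analyst who counts an untreated night. Nothing in the documents supports it. Under a d0 start, night 0 would also be available as a baseline.
- A reader might infer that chance imbalance in pre-treatment sleep (standard error sqrt(2/42.5) = 0.22 SD) is a further threat. It is ordinary sampling variation, already in the standard error of the t-test. Counting it beside the power gain counts the same thing twice. A single night would remove only part of it in any case.

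**Conclusion.** The point holds as a missed, inexpensive gain in precision. On the visible text, the only untreated night is not scheduled for recording and both actigraphic endpoints lack a pre-treatment value. The randomized comparison remains unbiased without it.

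The gain ranges from negligible to substantial: about 4% to 33% of the variance, or power of about 82% to 93% in place of 80%. This rests on 1:1 allocation, a true 80% power at 85 (not verifiable from the documents), a seven-night mean as the endpoint, interchangeable nights, and an ICC of 0.1 to 0.4 that the documents do not supply. The reading of the schedule is subject to the figure that cannot be seen. Cheap improvement.

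**What to change.** In Sections 3 and 4:
- Apply the actigraph on d0 once the ISI criterion is met.
- Label that night 'night 0 (baseline)' and exclude it from the outcome.
- State that recording continues through the night after the 7th session, eight nights in all.
- If the Section 4 figure already shows this, bring the text into line with it.

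In Section 14:
- Replace the plain t-test with an ANCOVA of each actigraphic endpoint on arm, with night-0 sleep time as covariate for sleep time and night-0 efficiency for efficiency.
- State in advance how a missing night-0 value is handled, for example with a missing-baseline indicator, so that no patient is dropped for lacking one.
- If the non-parametric alternative is kept, say how the baseline enters it.

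Cost: wording in three sections, one more night of wear, and researchers applying the watch on d0 instead of d1. Late admissions may lack night 0. A single night is a noisy baseline and may reflect residual medication, so the gain may fall at the low end. No new equipment is needed.
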